7.10.2 Site discontinuation

A site may be closed for the following reasons:

- The site is unlikely to be able to recruit sufficient patients within the agreed time frame
- The site does not respond to study management requests
- Repeated protocol violations

7.10.3 Study termination

The Sponsor reserves the right to modify or terminate the study at any time. All subjects recruited to the study prior to termination, including those who have been withdrawn, will be followed until 225 days after their last injection.

Possible reasons for termination are:

- Safety reasons –the incidence of AEs in this or any other study using the same IMP indicates a potential health risk for the subjects.
- New scientific knowledge becomes known that makes the objectives of the study no longer feasible/valid
- Unsatisfactory enrolment of patients

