3.3 Outcome measures/endpoints

3.3.1 Primary endpoints/outcomes

- Solicited AEs related to injection site tolerability during the week following each vaccine administration
- Unsolicited AEs through day 85

- Serious adverse events (SAEs) and AEs of special interest (AESIs) through 6 months after last vaccine dose
- Vital signs
- ECG
- Safety Laboratory including laboratory assessment of liver inflammation and function

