4 TRIAL DESIGN

This is a double-blind, randomised, placebo-controlled, dose-ascending study to evaluate the safety, tolerability and immunogenicity of Vaccine FP-02.2 in HBeAg-negative hepatitis B patients as an add-on treatment to entecavir or tenofovir.

Actively treated subjects will receive either a Low or High dose of Vaccine FP-02.2 with or without IC31®.

A placebo arm is included in the study. Safety and immunogenicity data generated from the placebo arm will allow comparison to data generated from the Vaccine FP-02.2 High and Low dose study arms. The placebo group is also necessary to understand the rate of natural HBsAg seroconversion in an untreated study arm. An IC31® alone arm is included in the study which will additionally allow comparison of safety and immunogenicity data with data generated from the Vaccine FP-02.2 High and Low dose/IC31® study arms.

Approximately of 60 subjects (excluding replacements for subjects deemed ineligible after dosing) will complete this trial and will be assigned equally to 6 study arms (approximately 10/study arm).

Screening will occur up to 28 days prior to the first injection.

Up to 3 days before the first injection, eligible subjects will be randomised to treatment arm as shown in Table 2, depending on the cohort.

Subjects will receive 3 injections at intervals of 28 days (Day 1, Day 29, and Day 57). On the days of the injections the subjects will stay in the clinic for at least 4 hours after the first injection and 2 hours after the second and third injections and be monitored closely including an assessment of local reactions at the injection site. Approximately 24 hours after the first injection, the subjects will be asked to attend the clinic for safety assessments. For subsequent injections, subjects will receive a telephone call approximately 24 hours after each injection for safety follow-up. The subjects will be asked to return to the clinic 7 days after each injection for further assessments as well as 28 days after the last injection (Day 85). A follow-up visit will be performed 6 months after the end of the treatment period (i.e. 6 months after the last dose).

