7.9 Allowed visit intervals

Allowed visit intervals are as follows:

- **screening and randomisation:** subjects must be screened 7 to 28 days (± 2 days) and can be randomised to treatment up to 3 days prior to the first injection.
- **first dose:** Visits 1 and 2 must be done on Days 1 and 2, respectively; Visit 3 may be done within ± 1 day of Day 8
- **second dose:** Visit 4 may be done within 28 days (± 7 days) of Visit 1; subjects must be phoned the day after Visit 4; Visit 5 should be done 7 (± 1 day) days after Visit 4
- **third dose:** Visit 6 may be done 28 days (± 7 days) after Visit 4; subjects must be phoned the day after Visit 6; Visits 7 and 8 should be done 7 (± 1 day) and 28 days (± 1 day) respectively after Visit 6
- **follow-up:** Visit 9 must be done 24 (± 4 weeks) weeks after the last dose (Visit 6)

The scheduled assessments may shift in instances where a visit window is used; subsequent visit dates should be recalculated from the date of the new visit. If a second dose visit is missed, the dose can be given 6 weeks after the first dose and noted as out of window. If the dose is later than 6 weeks, the second dose visit can be skipped and given at Visit 3 at 8 weeks as per schedule to avoid a delay in the schedule.

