7.12 End of trial

The end of the active study period is defined as the last Day 85 visit of the last subject participating in the trial. The end of the trial includes the late safety follow up period and is defined as the last Day 225 visit for the last subject participating in the trial. If the trial is terminated early, the trial ends when the Sponsor notifies the Investigator in writing that the trial has finished, or when the last subject attends the Day 255 visit, whichever is later. The Sponsor will notify the relevant competent authorities (CAs) and main Ethics Committees (ECs) of the end of a clinical trial within 90 days of its completion or 15 days if the trial is terminated early. A supplementary follow-up notification will be submitted to the relevant CAs and ECs after the last Day 225 visit.

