9.2 Operational definitions for (S)AEs

The occurrence of AEs will be assessed by non-directive questioning of the subject at each visit. Additionally, AEs volunteered by the subject during or between visits or detected through observation, physical examination, laboratory test or other assessments will be documented. Subjects will be instructed that they must immediately report any AEs, subjective complaints or objective changes in their well-being to the Investigator or the clinic personnel, regardless of the perceived relationship between event and test product.

All AEs must be fully recorded throughout the entire study period (from Screening Visit to Day 85) and will be entered into the subjects' eCRF, whether or not they are considered to be drug-related. Each AE should be described in detail: onset time and date, offset time and date, description of event, severity, relationship, action taken and outcome. From Day 85 and Day 225 only SAEs and AESIs will be collected.

Adverse events should be followed until recovery to the normal state has been achieved. In the event of a subject not returning to the clinical unit, every attempt will be made to contact the subject up to Day 85 after which the outcome of this event will be recorded as lost at follow-up.

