#### 12.6.1 Adverse Events

Adverse events will be coded using Version 20.0 or newer of MedDRA.

Treatment-emergent adverse events (TEAEs) are those which first occur or increase in severity or relationship probability to investigational product after the first dose of investigational product through 30 days after last dose of investigational product. Note that SAEs and AESIs are collected through 6 months after last dose of investigational product; therefore, all SAEs and AESIs will be summarized, not just treatment-emergent events.

All AEs which change in severity or relationship to investigational product are assigned a new start date and captured as a new record.

If more than 1 AE with the same preferred term is reported before the date of the dose of investigational product, then the AE with the greatest severity will be used as the benchmark for comparison to the AEs occurring during the study under the preferred term.

An overall summary of TEAEs, including the number and percentage of subjects who experience, and absolute count of treatment-emergent events for:

- Any TEAE
- Any TEAE by maximum severity
- Any TEAE considered possibly related to investigational product (defined as CRF response of "Reasonable Possibility")
- Any TEAE considered possibly related to investigational product by maximum severity
- Any SAEs
- Any SAEs considered possibly related to investigational product
- Any AEs with outcome of death
- Any AESIs (Hepatic flares and autoimmune conditions)
- Any TEAE leading to discontinuation of investigational product

The number and percentage of subjects reporting TEAEs, SAEs, or AESIs will be tabulated in the following ways by treatment group.

- By SOC and preferred term (including absolute count of events).
- By SOC, preferred term and maximum severity.
- By SOC and preferred term for TEAEs possibly related to investigational product in the opinion of the investigator (including absolute count of events).
- By SOC and preferred term for SAEs (including absolute count of events).
- By SOC and preferred term for possibly related SAEs (including absolute count of events).
- By SOC and preferred term for TEAEs leading to discontinuation of investigational product (including absolute count of events).
- By SOC and preferred term for AEs with fatal outcome (including absolute count of events).
- By SOC and preferred term for AESIs (including absolute count of events).

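### The end of safety follow-up is stated in conflicting ways, and the Day 85 limit on contact attempts makes no exception for SAEs and AESIs in subjects who do not return

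*Protocol*

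**What the plan says.** The safety endpoint in Protocol 3.3.1, repeated in SAP 7.1, includes "Serious adverse events (SAEs) and AEs of special interest (AESIs) through 6 months after last vaccine dose". SAP 12.6.1 gives the same period: "Note that SAEs and AESIs are collected through 6 months after last dose of investigational product". Protocol 4 sets the follow-up visit to match: "A follow-up visit will be performed 6 months after the end of the treatment period (i.e. 6 months after the last dose".

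The schedule states that visit differently. Protocol 7.7 puts Visit 9 at Day 225, with telephone calls about every 4 weeks from Day 85 until then. Protocol 7.9 and SAP 8.3 place it 24 weeks, give or take 4, "weeks after the last dose (Visit 6"), so the last dose is taken to be the third.

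Three other statements differ:

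- **Protocol 7.10.3**, on termination of the study by the sponsor: all recruited subjects, "including those who have been withdrawn, will be followed until 225 days after their last injection".
- **Protocol 7.12**, on the end of a trial terminated early: the later of the sponsor's written notice or "when the last subject attends the Day 255 visit, whichever is later". The same paragraph twice calls the final visit Day 225.
- **Protocol 9.2**, on a subject who stops attending: "every attempt will be made to contact the subject up to Day 85 after which the outcome of this event will be recorded". The outcome entered is then loss to follow-up. The same section collects SAEs and AESIs up to Day 225.

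**The concern.** Two separate problems arise. First, a site or sponsor acting on 7.10.3, 7.12 and 7.9 would reach different end dates for the same subject. The gap matters most after a termination, and safety is the first reason for termination that 7.10.3 lists.

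Second, the Day 85 limit in 9.2 stands in a section whose title covers serious events, and it exempts neither SAEs nor AESIs. The AESIs are hepatic flares and autoimmune conditions (Protocol Table 7), and Protocol 2.1.2 names immune-mediated death of infected hepatocytes as a theoretical risk in this first-in-man trial. A subject who stops attending with such an event unresolved could have it closed as lost well inside the endpoint period. For an event starting after Day 85 in a non-returner, the limit has already passed.

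SAP 12.6.1 tabulates SAEs and AESIs as numbers and percentages of subjects by arm, with no allowance for length of follow-up. With about 10 subjects per arm, one missed event moves an arm's proportion by about 10 percentage points (1/10).

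**Working it through.** **Inputs.** Doses on Days 1, 29 and 57 (Protocol 8.5); Visit 9 at 24 ± 4 weeks after Visit 6 (7.9, SAP 8.3) and at Day 225 (7.7); 225 days after the last injection (7.10.3); Day 255 (7.12); contact limit at Day 85 (9.2). The documents do not convert 6 months to days. I assume 365.25/2 = 182.6, with 182 to 184 as a reasonable range.

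**The plan's own figure.** 24 × 7 = 168, and 57 + 168 = 225. Day 225 is reproduced exactly.

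**Candidate ends of follow-up, nominal schedule.** Study day = day of last dose + interval.

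| Last dose received | 24 weeks after it | 6 months after it (about) | 225 days after it (7.10.3) | Days from dose to Day 225 | Days from dose to Day 85 |
|---|---|---|---|---|---|
| Dose 1, Day 1 | Day 169 | Day 184 | Day 226 | 224 | 84 |
| Dose 2, Day 29 | Day 197 | Day 212 | Day 254 | 196 | 56 |
| Dose 3, Day 57 | Day 225 | Day 240 | Day 282 | 168 | 28 |

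**Termination rule.** For three doses, 282 − 225 = 57 days past the nominal Visit 9. The latest permitted Visit 9 is 24 + 4 = 28 weeks, or 196 days, after the third dose. So 225 − 196 = 29 days lie beyond any permitted visit, whatever the dosing dates.

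**Day 255.** The flow chart has no such visit. On the nominal schedule the Visit 9 window runs from 57 + 140 = Day 197 to 57 + 196 = Day 253.

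**Fewer than three doses.** Protocol 7.9 allows a skipped second dose, 7.10.1 stops treatment in individuals, and SAP 8.3 expects some subjects with fewer than three doses. If Visit 9 runs from the dose actually received last, it falls on Day 169 or 197. If the study day governs, it is Day 225. The difference is 225 − 169 = 56 or 225 − 197 = 28 days, and no text decides.

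**24 weeks against 6 months.** Nominal shortfall: 182.6 − 168 = about 15 days. At the early edge of the window: 182.6 − 140 = about 43 days. At the late edge, 196 − 182.6 = about 13 days beyond.

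**Contact limit.** The last column of the table is the required contact period for a non-returning subject under 9.2 read literally: 84, 56 or 28 days, against about 183 in the endpoint.

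**The case against.** A reader might infer that the SAE/AESI endpoint is not collected over its stated period in anyone who stops treatment early. The documents do not support that:

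- The rule in 7.10.3 applies only to termination of the study, and 225 days is longer than 6 months, so it cannot cause under-collection.
- Protocol 7.10 encourages all subjects taken off treatment to stay in follow-up to the end of the study for late safety data. Section 7.10.1 continues safety collection after dosing stops for reactions or laboratory changes.
- An early stopper followed to Day 225 has 224 or 196 days after the last dose, which is more than 6 months.

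Other points on this side also carry weight. Day 255 is probably a slip for Day 225, and 7.12 defines the administrative end of the trial rather than each subject's follow-up. The 24-week and 6-month wordings describe the same visit and are mainly an approximation; the shortfall applies to completers too, and its 43-day figure is the extreme of the window. The rules are the same in every arm under blinding, and the analysis is descriptive, so no bias between arms is shown.

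It can also be said that the Day 85 sentence concerns only how an event's outcome is recorded, that the 4-weekly calls run to Day 225, and that 7.10.1 and 9.9 allow events to be followed to resolution. This narrows the problem but does not remove it. Continued follow-up is encouraged rather than required. For subjects who end participation, 7.10.1 provides a final examination and laboratory tests, with further follow-up only where a possibly related AE caused the exit. Follow-up under 9.9 is at the investigator's judgement. No passage clearly overrides the Day 85 limit for an SAE or AESI in someone who does not return.

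**Conclusion.** The point holds as an internal inconsistency that should be corrected. After termination, 7.10.3 implies Day 282 for a fully dosed subject against a Visit 9 at Day 225, and 7.12 points to a visit that does not exist. Visit 9 is ambiguous by 28 to 56 days for subjects with fewer than three doses. Under 9.2 as written, required contact with a non-returning subject can end 84, 56 or 28 days after dose 1, 2 or 3, although SAEs and AESIs are collected to Day 225 and the endpoint runs to 6 months.

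The contact gap is confined to subjects who do not return; it does not extend to early stoppers who remain in follow-up. The difference between 24 weeks and 6 months is minor. The figures assume the nominal dosing days, and comparisons with 6 months also assume about 183 days. How many subjects would fail to return cannot be judged from the documents.

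**What to change.** 1. Reconcile Protocol 7.9, 7.10.3 and 7.12 and SAP 8.3 to one end-of-follow-up definition. It should state what happens after one or two doses and should not bring those subjects' follow-up below the present Day 225 visit. Simply counting 24 weeks from the last dose received would do so, ending at Day 169 or 197. The documents do not show whether a longer period after termination was intended; if it was, visits or calls must be scheduled to cover it.
2. In Protocol 9.2, limit the Day 85 contact cut to events that are neither SAEs nor AESIs. For SAEs and AESIs, continue contact attempts to the end of follow-up, using the 4-weekly calls in 7.7.
3. In Protocol 3.3.1 and SAP 7.1, with matching text in SAP 12.6.1, restate 6 months as the period that Visit 9 delivers, 24 ± 4 weeks. The planned calls end at Day 225, so none falls at 6 months after a Day 57 dose (about Day 240).

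The cost is a protocol wording amendment, matching SAP text and a few more contact attempts for non-attenders. No dose or treatment rule changes.

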7.10.4 Replacement of subjects

Eligible subjects who are randomised and withdrawn before their second dose of IMP will be replaced. Subjects who have received two doses of IMP who are subsequently withdrawn from the study will not be replaced.

7.11 Storage and analysis of samples

It is the responsibility of the trial site to ensure that samples are appropriately labelled in accordance with the trial procedures to comply with local legislation. Biological samples collected from participants as part of this trial will be transported, stored, accessed and processed in accordance with local legislation relating to the use and storage of human tissue for research purposes. Information for specific handling and storage conditions can be found in the laboratory manual.

7.11.1 Safety laboratory

Blood and urine samples will be collected for safety laboratory tests and screening for alcohol, drugs of abuse and HIV, HDV and HCV infection at the times indicated in the flow chart (see Table 1 Flow chart). The analytes listed in Table 5 will be determined.

Clinical laboratory tests (see Table 5) will be performed at local site hospital laboratories. Procedures for sample collection, processing, and storage will be described in a separate laboratory manual. Additional and repeat testing may be performed at the discretion of the Investigator.

Table 5 Clinical laboratory safety test analytes

Panel	Parameters	
Haematology	White blood cells (leukocytes)	Neutrophils [a]
	Red blood cells (erythrocytes)	Lymphocytes [a]
	Haemoglobin	Monocytes [a]
	Haematocrit	Eosinophils [a]
	Mean corpuscular volume	Basophils [a]
	Mean corpuscular haemoglobin	Platelets
	Mean corpuscular haemoglobin concentration	
Serum biochemistry	Sodium	Aspartate transaminase (AST)
	Potassium	Alkaline phosphatase (ALP) [b]
	Urea	Alanine aminotransferase (ALT)
	Creatinine	Creatine kinase [c]
	Albumin	Gamma-glutamyl transferase (gamma glutamyl transpeptidase) (GGT)
	Calcium	Lactate dehydrogenase
	Phosphate	Total and direct bilirubin
	Glucose	
	Total protein	
	C-reactive protein	
Coagulation	International normalized ratio of prothrombin time (INR)	
Urinalysis	Protein	Leukocyte esterase
	Bilirubin	Red blood cells
	Urobilinogen	pH
	Ketones	Nitrites
	Glucose	Specific gravity
Urine microscopy [d]	Microscopy to be performed if clinically indicated (as per local procedures)	
Viral serology [d]	Human immunodeficiency virus (HIV I and II)	Hepatitis C virus (HCV) antibodies
		Hepatitis D virus (HDV) antibodies
Drugs of abuse and alcohol screen [d]	Amphetamine/ecstasy	Opiates
	Ethanol	Benzodiazepines
	Cannabinoids	Methadone metabolites
	Cocaine	Barbiturates
	Urine creatinine	
Serum/urine pregnancy test [e]	Beta human chorionic gonadotropin	

[a] Given as both absolute count and as a percentage of total leukocyte count.

[b] Alkaline phosphatase iso-enzymes (liver-specific and bile duct specific) will be measured if original alkaline phosphatase test result is above the upper limit of normal.

[c] Creatine kinase MB or Troponin T will be measured where clinically indicated.

[d] At Screening Visit only.

[e] A serum pregnancy test will be performed in all women of childbearing potential at the Screening Visit. Serum β HCG concentrations above 5 mIU/mL. Urine pregnancy tests will be performed during the remainder of the study at the times indicated in the flow chart.

7.11.2 Immunology

Blood samples will be processed to isolate, cryopreserve and store PBMC. This may be conducted at a central laboratory at Altimmune or at Investigator sites. Further details can be found in the laboratory manual.

Subsequent primary immunological analysis (IFNy ELISpot) will be conducted at Altimmune. Any cryopreserved PBMC prepared and stored at Investigator sites will be transferred to Altimmune prior to analysis.

Other specialist laboratories may be used for exploratory immunological analyses and for HLA genotyping. A PBMC sample from either the screening visit or Visit 1 will be used for HLA genotyping in consenting subjects. PBMC samples isolated at other time points may be used for other genotyping as required.

7.11.3 Virology

Blood samples will be collected for the assessment of virological parameters (HBsAg, HBsAb, HBV DNA) at the times indicated in the flow chart (see Table 1 Flow chart). Isolation of serum or plasma will be performed at the clinical site following methods detailed in the laboratory manual. Serum and plasma will be stored at the clinical site under appropriate conditions (further details are provided in the laboratory manual) until shipment to Altimmune laboratories. Batched samples will be sent from Altimmune laboratories to King's Liver Labs for virological analysis as detailed in the laboratory manual.

7.11.4 Sampling handling and storage

The handling of the samples will be described in a separate laboratory manual.

Samples will be retained for a period up to 10 years and will only be used for purposes described in this protocol.

7.11.5 Blood volume

The estimated blood volumes collected from each subject during the study for safety, immunology and virology tests as described in Sections 7.11.1, 7.11.2, and 7.11.3, respectively, are presented in Table 6 Approximate Blood volumes [a].

Table 6 Approximate Blood volumes [a].

	Sample Volume	Number of Samples	Total Volume (mL)
Safety			
Serum biochemistry [b]	5.0	8	40.0
Haematology [b]	2.0	8	16.0
Coagulation [b]	2.0	8	16.0
Serum pregnancy test [b,c]	3.5	1	3.5
Serology (HCV/HIV I and II, HDV) [b]	3.5	1	3.5
Immunoanalysis			
Cellular immunoanalysis (PBMC) [d]	40	9	360.0
Virology			
HBsAg, HBsAb, HBV DNA quantitative [e]	4.0/8.0 [f]	6	32.0
Total [a]			
Male subjects			467.5
Female subjects			471.0

HBsAg = hepatitis B surface antigen; HBsAb = antibody to hepatitis B surface antigen; HCV = hepatitis C virus; HDV = hepatitis D virus; HIV = human immunodeficiency virus; PBMC = peripheral blood mononuclear cells.

[a] Sample volumes are based on direct venipuncture; where a cannula is used an extra 1mL will be drawn and discarded. Specific volumes for safety analysis may vary from site to site.

[b] Analysis to be performed by site-specific Hospital Laboratories.

[c] All women of childbearing potential; serum pregnancy test will be conducted at the Screening Visit.

[d] Isolation of PBMC may be performed at a central laboratory, at Altimune, or at the Investigator site.

[e] Analysis to be performed by King's Liver Labs which is a Clinical Pathology Accreditation UK Ltd. (CPA UK Ltd.) enrolled Laboratory.

[f] 4.0 mL of blood will be collected for virology except at screening and visit 9 when 8.0mL of blood will be collected.

The planned blood volume is not greater than 150mL each month. However, the number of samples collected and the volume required for each analysis may change during the study (i.e. if additional samples are collected for repeated assessments). Extra blood samples for safety assessments will be taken only as and when needed. No more than an extra 50mL blood will be taken each month for immunology and virology assessments.

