7.2.1 Screening

The following screening assessments will be conducted between days -28 and -1:

- Sign informed consent
- Obtain medical history and demographic data
- Review of eligibility criteria
- Laboratory studies:
 - HBsAg monitoring
 - HBsAb monitoring
 - HBV DNA monitoring
- Vital signs
- Physical examination including measurement of weight and height
- Fibroscan
- Serum pregnancy test in women of childbearing potential
- Safety laboratory tests
- Urine dipstick test for drug abuse and alcohol screen
- Test for HIV, HDV and HCV
- Documentations of AEs
- Blood for cell-mediated immunity (CMI)
- 12-lead ECG

Patients who pass screening but are not dosed within 28 days may be re-screened once.

Subjects who have given their written informed consent will be allocated unique subject identification numbers in sequential order according to their admission to the study within each site by Interactive Response Technology (IRT). This number will be used for identification throughout the study and will not be used for any other participant.

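### The stated planned blood volume of at most 150 mL a month is not what the schedule delivers: 155 mL in 29 days on nominal dates, about 204 mL within the permitted visit windows

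*Protocol*

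**What the plan says.** Protocol 7.11.5 lists sample volumes and counts in Table 6, with totals of 467.5 mL for men and 471.0 mL for women. It then states: "The planned blood volume is not greater than 150mL each month". The section does not say whether a month is a dosing cycle, a calendar month or any run of 28 to 31 days.

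The same paragraph warns that sample numbers and volumes may change, and adds: "No more than an extra 50mL blood will be taken each month for immunology and virology assessments". A footnote to Table 6 says that safety volumes may differ between sites.

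The visit dates can move. Under flow-chart footnote 6 and Section 7.9, Visit 4 is due 28 days (± 7) from Visit 1 and Visit 6 is due 28 days (± 7) after Visit 4. Visits 5 and 7 follow their injection by 7 days (± 1), and later visits are recalculated from the actual dates.

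The screening interval is given in two ways. Section 7.2.1 says: "The following screening assessments will be conducted between days -28 and -1". The flow chart agrees, and SAP 8.3 repeats the flow chart's version. Section 7.9 instead sets screening 7 to 28 days (± 2) before the first injection.

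**The concern.** Visits 4, 6 and 8 each combine a 40 mL cell sample, the safety laboratory bloods and a virology sample. They are nominally 28 days apart, with another large draw 7 days after each injection. Two of these heavy visits and the draw between them already come close to 150 mL, so the stated figure looks too low.

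This sentence is the protocol's only statement of the monthly blood draw. A site or ethics committee relying on it would understate the burden on a subject. No dose, endpoint or analysis depends on it.

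**Working it through.** **Inputs (Table 6 and its footnotes).**
- Cell samples: "Cellular immunoanalysis (PBMC) [d] 40 9 360.0", so 40 mL each.
- Safety laboratory: "Serum biochemistry [b] 5.0 8 40.0", "Haematology [b] 2.0 8 16.0" and "Coagulation [b] 2.0 8 16.0", so 5 + 2 + 2 = 9 mL per visit.
- Virology: "4.0 mL of blood will be collected for virology except at screening and visit 9 when 8.0mL of blood will be collected".
- Screening only: 3.5 mL for serology, and 3.5 mL for the serum pregnancy test in women of childbearing potential.

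**Volume per visit (draws placed by the flow chart).**

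| Visit | Nominal day | Sum | mL |
|---|---|---|---|
| Screening | before Day 1 | 40 + 9 + 8 + 3.5 | 60.5 (64 with pregnancy test) |
| 1 | 1 | 40 + 4 | 44 |
| 3 | 8 | 40 + 9 | 49 |
| 4 | 29 | 40 + 9 + 4 | 53 |
| 5 | 36 | 40 + 9 | 49 |
| 6 | 57 | 40 + 9 + 4 | 53 |
| 7 | 64 | 40 + 9 | 49 |
| 8 | 85 | 40 + 9 + 4 | 53 |
| 9 | 225 | 40 + 9 + 8 | 57 |

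**Reproducing the plan's figure.** 60.5 + 44 + 49 + 53 + 49 + 53 + 49 + 53 + 57 = 467.5 mL; adding 3.5 gives 471.0 mL. Both match Table 6, so the split by visit is the protocol's own.

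**Nominal dates, by dosing cycle.** Days 1–28: 44 + 49 = 93 mL. Days 29–56: 53 + 49 = 102 mL. Days 57–84: 53 + 49 = 102 mL. All are below 150 mL.

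**Nominal dates, rolling 29 days (both end days counted).** Days 1–29: 44 + 49 + 53 = 146 mL. Days 29–57: 53 + 49 + 53 = 155 mL. Days 57–85: 53 + 49 + 53 = 155 mL. The excess is 5/150 = 3.3%.

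**Permitted windows, screening not counted.**
- Visit 1 on Day 1, Visit 3 on Day 8, Visit 4 on Day 22 (28 − 7 days after Visit 1), Visit 5 on Day 28 (7 − 1 days after Visit 4): 44 + 49 + 53 + 49 = 195 mL in Days 1–28, which is 30% over.
- Visit 6 placed 21 days after Visit 4, and Visit 7 placed 6 to 8 days after Visit 6: 53 + 49 + 53 + 49 = 204 mL in 28 to 30 days, which is 36% over.

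**Permitted windows, screening counted.**
- Section 7.9: screening can be 7 − 2 = 5 days before Visit 1. With Visit 4 on Day 22 the span is 5 + 21 + 1 = 27 days: 60.5 + 44 + 49 + 53 = 206.5 mL (210 mL with the pregnancy test). Visit 5 cannot be added within 31 days, because the span would be 5 + 27 + 1 = 33 days. So 206.5 / 210 mL is the maximum for any span of 27 to 31 days.
- Flow chart and Section 7.2.1: screening on Day -1, Visit 4 on Day 22 and Visit 5 on Day 28 span 1 + 27 + 1 = 29 days: 206.5 + 49 = 255.5 mL (259 mL with the pregnancy test), about 70% to 73% over.

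**The case against.** **The month may mean a dosing cycle.** The schedule runs in 28-day cycles, and on nominal dates every cycle is well under 150 mL. The 155 mL arises only when the first draw of the next cycle is included. This stands for nominal dates. It does not rescue the figure within the windows, where Days 1 to 28 can hold 195 mL.

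**The on-schedule excess is small.** It is 5 mL in a table of approximate volumes that may vary by site. That stands too: 155 mL alone could pass as rounding. An excess of 30% or more could not.

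**Planned may mean nominal dates only.** The 204 mL case needs Visit 6 brought forward by its full 7 days. That is a fair reading of the word, but the protocol permits those dates without treating them as deviations. The 50 mL allowance does not cover the gap, because it is for extra samples and not for scheduled draws. In any case, 204 mL exceeds 150 + 50 = 200 mL.

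**Stronger readings that the documents do not support.** A reader might infer that nearly every subject exceeds 150 mL in a calendar month. On nominal dates, with Day 1 placed on each date of a four-year span, the share is 32% with screening 28 days before dosing, 40% at 21 days, 63% at 14 days and 84% at 7 days. The near-universal statement fits only a rolling span of 29 to 31 days. A reader might also take 210 mL as the true maximum. That holds under Section 7.9 but not under the flow chart's Day -1, where it is 259 mL. Finally, nothing here shows harm to subjects or an error in the Table 6 totals.

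**Conclusion.** Wrong as written; minor. With the month undefined, the 150 mL statement is true for nominal dosing cycles (93, 102 and 102 mL). It is not true for a rolling 29-day span on schedule (155 mL), nor for what the visit windows allow (195 mL in Days 1 to 28; 204 mL in 28 to 30 days). These figures do not depend on when screening takes place. The figures that include screening (206.5 / 210 mL or 255.5 / 259 mL) depend on which of the two screening intervals applies, and the documents do not settle that.

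The result assumes the Table 6 volumes as printed, draws placed by the flow chart, and days counted inclusively. The 1 mL cannula discard and any repeat samples would add to the totals.

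**What to change.** In Protocol 7.11.5, define the month. Reconcile the screening interval between the flow chart (with its footnote 6), Section 7.2.1 and Section 7.9, and carry the result into the SAP flow chart and SAP 8.3. Then restate the planned monthly figure as the maximum under the permitted windows. For a rolling month this is about 155 mL on nominal dates once dosing has started, about 204 mL within the windows without screening, and the screening-inclusive maximum that follows from the reconciled interval. Whether the limit, the volumes or the windows should change is for the sponsor and investigators; this point asks only that they agree.

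The subject information was not available for this review. Check it, and align it only if it repeats the 150 mL figure.

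The cost is one restated sentence plus the alignment of the screening interval. The stated figure becomes less favourable, and no analysis changes.
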